10.0 Statistical Design

Endpoint and Design: The primary objective of this phase II study is to assess the activity of the combination of the Bruton's tyrosine kinase (Btk) inhibitor PCI-32765 and rituximab in Chronic Lymphocytic Leukemia (CLL) in high-risk CLL patients that have received prior therapy. Untreated CLL patients with high-risk disease based on the presence of a 17p deletion or *TP53* mutation will also be eligible. The primary endpoint is progression-free survival (PFS). Denote the median (T) = m_H , for the historical data (H) and m_E , for the experimental (E) trial, where T is time to progression in month. We assume that, T is distributed exponentially with median m_H , with the historical regimen and median m_E , with the new treatment. Under a Bayesian model, we will further assume that m_H , follows an inverse gamma (IG) prior with parameters (18, 85) reflecting the historical data (i.e., 20 patients with chromosome 17 abnormalities who had a median PFS of 5 months)⁶, and m_E , follows IG(2.25, 6.25) with the same mean as m_H , but with a much larger variance of 100 to reflect much greater uncertainty about PFS. Progression free survival is defined as the time interval from treatment to progressive disease or death, whichever happens earlier. Patients in complete remission (CR), partial remission (PR) or stable disease (SD) are all counted as progression-free. Due to the characteristic activity of PCI-32765, which typically induces a transient lymphocytosis during the first months of therapy⁷, which is not causing any symptoms and which is due to a re-distribution of CLL cells from the tissue compartments (bone marrow, secondary lymphatic tissues) into the peripheral blood, increases in lymphocyte counts can be expected (although in this combination with rituximab are less likely) and will not be considered as a sign of progressive disease.

Interim Analysis on PFS: We will accrue 40 patients and will monitor the PFS continuously, accrual will be terminated early if $\Pr(m_H + 2 \text{ months} < m_E \mid \text{data}) <$

0.01. The design operating characteristics based on 1000 simulations are summarized in Table 1. (Accrual of 40 patients with a rate = 3/month, 6 months additional follow-up). For example, the trial will stop early with 97.5% chance (23.3 patients in average) if the median PFS is 3 months, but stop early with 7.8% chance (38.6 patients in average) if the median PFS is 6 months.

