Table1. Simulation study with maximum 40 patients:

True median PFS	Pr(stop)	Mean number of patients (25%, 75%)
3 months	0.975	23.3 (14, 33)
4 months	0.632	31.8 (24, 40)
5 months	0.240	36.6 (40, 40)
6 months	0.078	38.6 (40, 40)
7 months	0.038	39.1 (40, 40)
8 months	0.018	39.6 (40, 40)

Interim Analysis on Toxicity: The probability of toxicity (grade 3 or 4) will be monitored based on the Bayesian model (beta-binomial) by assuming a priori probability of toxicity following beta(1,1). The trial will be terminated if $\text{Prob}(\text{toxicity} > 0.25 \mid \text{data}) > 0.90$. Following this rule, the trial will be terminated if $(\# \text{ patients with toxicities})/(\# \text{ patients evaluated}) \geq 2/3, 3/6, 4/9, 5/12, 6/15, 7/18, 8/22, 9/25, 10/28, 11/31, 12/35, 13/38, \text{ or } 14/40$. The operating characteristics for toxicity are summarized in Table 2.

Table 2. Operating characteristics based on 10000 simulation study

True Prob(tox)	Pr(stop early)	Median # Pts (25%, 75%)
0.05	<0.01	40 (40, 40)
0.10	0.04	39 (40, 40)
0.15	0.11	36 (40, 40)
0.25	0.41	28 (9, 40)
0.35	0.79	17 (4, 28)
0.45	0.97	9 (3, 10)
0.55	>0.99	6 (3, 7)

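### Table 2's column of median patient numbers holds means, and the printed toxicity boundary 11/31 stops one patient short of the stated 0.90 rule, which also stops at 11/32

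*Combined protocol and SAP*

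**What the plan says.** Section 10.0, Interim Analysis on Toxicity, monitors grade 3 or 4 toxicity with a beta-binomial model, "by assuming a priori probability of toxicity following beta(1,1"). The trial stops if the posterior probability that the toxicity rate exceeds 0.25 is above 0.90. The plan then gives the boundaries said to follow from this rule, as toxicities over patients evaluated: "2/3, 3/6, 4/9, 5/12, 6/15, 7/18, 8/22, 9/25, 10/28, 11/31, 12/35, 13/38", and finally 14/40. The maximum sample size comes from the PFS paragraph: "We will accrue 40 patients".

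Table 2 is titled "Operating characteristics based on 10000 simulation study". For seven true toxicity rates it prints the probability of stopping early and a column headed "Median # Pts (25%, 75"%). The entries in that column are 40, 39, 36, 28, 17, 9 and 6, each with two quartiles. The parallel column in Table 1 is headed "Mean number of patients (25%, 75"%).

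**The concern.** Three rows of Table 2 are impossible as labelled. At 0.10 and 0.15 the stated median is below both quartiles. At 0.25 only 41% of trials stop early, so at least 59% enrol all 40 patients and the median must be 40, not 28.

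The boundary list presents itself as a consequence of the probability rule, but one entry does not agree with it. If list and rule differ, there is a reachable outcome at which the trial has two opposite instructions.

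These are the action thresholds of the safety rule and the figures by which a review board judges how many patients would be exposed before it acts. As printed, 17 patients looks like the typical enrolment at a 35% toxicity rate, when the median is 9. At 25%, 28 looks typical, when more than half of trials run to 40.

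**Working it through.** **Inputs (all from section 10.0).** Prior beta(1,1); toxicity threshold 0.25; stop if the posterior probability is above 0.90; maximum 40 patients; the 13 printed boundaries; Table 2.

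**Boundaries.** With x toxicities in n patients the posterior is Beta(1+x, 1+n−x), so

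Pr(rate > 0.25 | x, n) = 1 − F(0.25; 1+x, 1+n−x), with F the beta distribution function.

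For each x from 2 to 14, the largest n up to 40 at which this exceeds 0.90 is 3, 6, 9, 12, 15, 18, 22, 25, 28, **32**, 35, 38, 40. Twelve of the 13 match the printed list, so the model is the intended one. The exception is x = 11:

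| Toxicities / patients | Posterior probability | Rule |
|---|---|---|
| 11/31 | 0.9196 | stop |
| 11/32 | 0.9013 | stop |
| 11/33 | 0.8807 | continue |

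The printed 11/31 does satisfy the rule, but it is not the last n at which 11 toxicities stop the trial. A different prior does not explain it: Beta(0.5, 0.5) gives 11/31 but also 8/21, 9/24 and 12/34, which disagree with the list. Beta(0.5, 1.5) and Beta(0.25, 0.75) fit worse.

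**Operating characteristics.** The distribution of the number of patients at stopping was computed exactly, by adding one patient at a time and removing outcomes at or above the boundary. The printed list was used, with looks after every patient from the third. Then mean = Σ n × Pr(stop at n) + 40 × Pr(never stop).

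| True toxicity | Printed Pr(stop) | Exact Pr(stop) | Printed as median | Exact mean | Exact median |
|---|---|---|---|---|---|
| 0.05 | <0.01 | 0.009 | 40 | 39.7 | 40 |
| 0.10 | 0.04 | 0.040 | 39 | 38.6 | 40 |
| 0.15 | 0.11 | 0.106 | 36 | 36.4 | 40 |
| 0.25 | 0.41 | 0.404 | 28 | 27.9 | 40 |
| 0.35 | 0.79 | 0.799 | 17 | 16.7 | 9 |
| 0.45 | 0.97 | 0.975 | 9 | 9.1 | 5 |
| 0.55 | >0.99 | 0.999 | 6 | 5.65 | 3 |

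The stopping probabilities reproduce to within about 0.01. (The exact column counts a stop at patient 40; without it, the values at 0.35 and 0.45 are 0.795 and 0.973.) All seven printed patient numbers are the means after rounding.

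**Start of monitoring.** The plan states no minimum number of patients. Starting at the third is an assumption, taken from the first listed boundary, 2/3. The rule as written would also stop at 1/1 (posterior 0.9375), but then Pr(stop) at a true rate of 0.05 would be at least 0.05, against the printed <0.01. If stopping at 2/2 were allowed, the mean at 0.55 would be 5.35, which does not round to the printed 6.

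**Effect of the boundary entry.** Replacing 11/31 by 11/32 moves Pr(stop) from 0.4044 to 0.4069 at a true rate of 0.25 and from 0.7987 to 0.8013 at 0.35. Under the printed list, the chance of being at exactly 11 toxicities in 32 patients is 0.04% at a true rate of 0.15, 0.7% at 0.25, 1.4% at 0.35 and 0.7% at 0.45.

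**The case against.** The best case on the other side is that both slips are editorial. The expected number of patients is printed correctly and only its heading is wrong. The stopping probabilities, which matter most for judging the rule, are sound. The boundary slip concerns one outcome, where the posterior passes the cutoff by 0.0013, and the list would still stop the trial on a twelfth toxicity by patient 35. The plan also states the probability rule itself, and the Statistical Analysis paragraph describes a website that evaluates monitoring rules automatically. All of this stands as a limit on the size of the problem.

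Two parts do not remove it. The website text first covers the efficacy rules, then refers to rules set out later in the document, and none follow. It is therefore unclear whether the toxicity rule is automated or staff work from the printed list.

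It could also be said that the list is a schedule of looks, so that 32 patients is never examined. That reading fits the rounded means too. But the plan sets no such schedule, and every other entry is exactly the largest stopping n for its count. A list of limits explains that; a look schedule would make it a coincidence.

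One further objection is fair: the replacement medians depend on the look schedule. With looks only at the printed sample sizes, the median at 0.45 is 6 rather than 5; the others are unchanged.

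**Conclusion.** Both errors are confirmed. The mislabelled column needs no model to detect: three of its seven rows contradict their own quartiles or stopping probability. That the values are means follows from the exact calculation, assuming monitoring from the third patient. The boundary error follows directly from the stated prior, threshold and cutoff: at 11 toxicities in 32 patients the rule stops and the list continues.

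The practical effect is small. Stopping probabilities change by less than 0.3 percentage points, and the conflicting outcome arises in at most about 1.4% of trials at the tabulated toxicity rates. It merits correction because it sits in the trial's safety rule and the two statements of that rule should not disagree.

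**What to change.** Head the last column of Table 2 as the mean, as in Table 1. Alternatively, print the medians 40, 40, 40, 40, 9, 5 and 3 and state that monitoring runs after every patient from the third. In the boundary list, change 11/31 to 11/32 so that it follows the rule it cites. These are two text corrections with no operational cost.

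When Table 2 is reissued, its quartiles should be checked as well. At true rates of 0.35, 0.45 and 0.55 the plan prints (4, 28), (3, 10) and (3, 7), whereas the same exact calculation gives (3, 31), (3, 12) and (3, 6).

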11.0 Amendments, Deviations, Regulatory

Protocol Amendments

Any amendment to this protocol must be agreed to by the Principal Investigator and reviewed by Pharmacyclics. Amendments should only be submitted to IRB/EC after consideration of Pharmacyclics review. Written verification of IRB/EC approval will be obtained before any amendment is implemented.

Protocol Deviations

When an emergency occurs that requires a deviation from the protocol for a subject, a deviation will be made only for that subject. A decision will be made as soon as possible to determine whether or not the subject (for whom the deviation from protocol was effected) is to continue in the study. The subject's medical records will completely describe the deviation from the protocol and state the

reasons for such deviation. In addition, the Investigator will notify the IRB/EC in writing of such deviation from protocol.

Investigator Responsibilities

Investigator responsibilities are set out in the ICH guideline for Good Clinical Practice (GCP) and in the US Code of Federal Regulations. Investigators must enter study data into MDACC's PDMS. The Investigator will permit study-related monitoring visits and audits by MDACC's ORERM, Pharmacyclics or its representatives, IRB/EC review, and regulatory inspection(s) (e.g., FDA, EMEA, TPP), providing direct access to the facilities where the study took place, to source documents, to CRFs, and to all other study documents. The Investigator, or a designated member of the Investigator's staff, must be available at some time during monitoring visits to review data and resolve any queries and to allow direct access to the subject's records (e.g., medical records, office charts, hospital charts, and study related charts) for source data verification. The data collection must be completed prior to each visit and be made available to MDACC ORERM and the Pharmacyclics representative so that the accuracy and completeness may be checked.

Institutional Review Board/Ethics Committee Approval

The protocol for this study has been designed in accordance with the general ethical principles outlined in the Declaration of Helsinki. The review of this protocol by the IRB/EC and the performance of all aspects of the study, including the methods used for obtaining informed consent, must also be in accordance with principles enunciated in the declaration, as well as ICH Guidelines, Title 21 of the Code of Federal Regulations (CFR), Part 50 Protection of Human Subjects and Part 56 Institutional Review Boards. The Investigator will be responsible for preparing documents for submission to the relevant IRB/EC and obtaining written approval for this study. The approval will be obtained prior to the initiation of the study. The approval for both the protocol and informed consent must specify the date of approval, protocol number and version, or amendment number. Any amendments to the protocol after receipt of IRB/EC approval must be submitted by the Investigator to the IRB/EC for approval. The Investigator is also responsible for notifying the IRB/EC of any serious deviations from the protocol, or anything else that may involve added risk to subjects. Any advertisements used to recruit subjects for the study must be reviewed and approved by the IRB/EC prior to use.

Informed consent

The Investigator must obtain informed consent of a subject or his/her designee prior to any study related procedures as per GCPs as set forth in the CFR and ICH guidelines. Documentation that informed consent occurred prior to the subject's entry into the study and the informed consent process should be recorded in the subject's source documents. The original consent form signed and dated by the subject and by the person consenting the subject prior to the subject's entry into the study, must be maintained in the Investigator's study files.

Study records requirements

The Investigator must ensure that the records and documents pertaining to the conduct of the study and the distribution of the study drug, that is copies of CRFs and source documents (original documents, data, and records (e.g., hospital records; clinical and office charts; laboratory notes; memoranda; subject's diaries or evaluation checklists; pharmacy dispensing records; recorded data from automated instruments; copies or transcriptions certified after verification as being accurate copies; microfiches; photographic negatives, microfilm, or magnetic media; x-rays; subject files; and records kept at the pharmacy, at the laboratories, and at medico-technical departments involved in the clinical study; documents regarding subject treatment and study drug accountability; original signed informed consents, etc.)) be retained by the Investigator for as long as needed to comply with national and international regulations (generally 2 years after discontinuing clinical development or after the last marketing approval). The Investigator agrees to adhere to the document/records retention procedures by signing the protocol.

Premature Discontinuation of Study

The responsible local clinical Investigator, as well as Pharmacoclics, has the right to discontinue this study at any time for reasonable medical or administrative reasons in any single center. Possible reasons for termination of the study could be but are not limited to:

1. Unsatisfactory enrollment with respect to quantity or quality.
2. Inaccurate or incomplete data collection.
3. Falsification of records.
4. Failure to adhere to the study protocol.

Concomitant Medications and Treatment			X								
Serum Chemistry ^b			X								
PT/PTT/INR ^c			X								
Hematology ^d			X								
CLL Panel ^e			X								
Bone Marrow Aspiration and biopsy ^f	X										
Electrocardiogram ^g	X										
CT Scans ^h	X							X			
Pregnancy Test			X								
Optional correlative laboratory studies (blood samples) ⁴			X	X	X ^r						
Clinical Visits at UT MD Anderson Cancer Center ⁱ				X	X				X	X	
Hematology and Serum Chemistry ^j				X ^k					X	X	X
PT, PTT, INR						X ^l					X
Beta-2-microglobulin, lymphocyte subset, immunoglobulin levels ^m								X			X

Bone Marrow Aspiration ⁿ								X			X
CT Scans ^o							X	X			X
Optional Quality of Life Questionnaire ^p						X					
Optional correlative laboratory studies (blood samples) ^q			X	X	X ^r						

- a) Includes vital signs (within 7 days of Day 1).
- b) Includes sodium, potassium, calcium, magnesium, phosphorus, BUN, creatinine, glucose, albumin, total protein, alkaline phosphatase, total bilirubin, ALT, uric acid, and immunoglobulin levels, Beta-2 microglobulin within 7 days of Day 1.
- c) Prothrombin Time/PT; Partial Thromboplastin Time/PTT; and International Normalized Ratio/INR within 7 days of Day 1.
- d) Complete CBC and differential and peripheral blood lymphocyte subset and immunoglobulin levels (within 7 days of registration).
- e) Flow cytometry assessment for peripheral CLL cells and lymphocyte subpopulations (CD3, CD4, CD8, CD19,CD16/56 cells) within 7 days of Day 1.
- f) Within one month from registration. Bone marrow will be evaluated by flow cytometry for clonality and for IgVH mutation studies (unless known) ZAP-70 expression (unless known), cytogenetic and genomic abnormalities by FISH.
- g) Within one month
- h) CT scans of the chest, abdomen and pelvis within two months from Day 1.
- i) Includes vital signs and physical exam at The University of Texas MD Anderson Cancer Center during the first 4 weeks, and then after, cycles 2,3,4,6,9 and 12 (+/- 1 month). If patients stay on the study past 12 cycles, they return for clinic visits at UT MD Anderson for clinical assessment and laboratory workup (hematology and clinical chemistry) every 3 months (+/- 1 month) for cycles 13 through 36, and every 6 months (+/1 month) thereafter.
- j) Complete blood counts (white blood cell, hemoglobin, platelets and differential) and Serum chemistry: basic metabolic profile (sodium, potassium, chloride, CO2, BUN, creatinine and glucose) will be monitored once weekly for first 4 weeks (+/-3 Days), and then every 4 weeks thereafter. If patients stay on the study past 12 cycles, they will have these laboratory tests (hematology and clinical chemistry) done every 3 months (+/- 1 month) for cycles 13 through 36, and every 6 months (+/- 1 month) thereafter during their clinic visit.
- k) Once every 4 weeks thereafter until the end of cycle 12.
- l) PT, PTT, INR will be monitored after 1,3,6 and 12 cycles (+/- 1 month) and if patients stay on study past 12 cycles, once every 12 cycles (+/- 1 month).
- m) Will be performed and evaluated by flow cytometry after 3, 6 and 12 cycles (+/- 1 month) and if patients stay on study past 12 cycles, once every 12 cycles (+/- 1 month).
- n) If patients' bone marrow tests are consistent with a complete remission, no further bone marrow testing is mandatory, and will be ordered at the treating physicians' direction.
- o) CT scans of chest and abdomen after 3 or 6, and 12 cycles (+/- 1 month), and once every 12 cycles thereafter. If patients stay on the study past 24 cycles, once every 12 cycles only inpatients with measurable disease, as determined by the treating physician.
- p) Questionnaire collected at baseline, after 3, 6, 12 and every 6 cycles.
- q) Optional correlative laboratory studies (blood samples) will be done before study entry, and after weeks 1, 2, 3, 4 (+/- 3 days).
- r) Optional correlative laboratory studies(blood samples) at 12 weeks (cycle 3) (+/- 1 month) only and again in patients who fail to respond to therapy after 6 months or at the time of relapse.

Time and Events Schedule: Screening

Evaluation or Procedure	Screening (60 days)	Screening (30 Days)	Screening (14 Days)	Screening (7 Days)
Clinical Assessments	(Day -60)	(Day -30)	(Day -14)	(Day -7 to -1)
Informed Consent				X
Physical Evaluation ^a				X
ECOG/WHO Eval				X
Height/Weight				X
Concomitant Medications and Treatment				X
Serum Chemistry ^b				X
PT/PTT/INR ^c				X
Hematology ^d				X
CLL Panel ^e				X
Bone Marrow Aspiration and biopsy ^f		X		
Electrocardiogram ^g		X		
CT Scans ^h	X			
Pregnancy Test				X
Optional correlative laboratory studies (blood samples) ^q				X

- a) Includes vital signs (within 7 days of Day 1).
- b) Includes sodium, potassium, calcium, magnesium, phosphorus, BUN, creatinine, glucose, albumin, total protein, alkaline phosphatase, total bilirubin, ALT, uric acid, and immunoglobulin levels, Beta-2 microglobulin within 7 days of Day 1.
- c) Prothrombin Time/PT; Partial Thromboplastin Time/PTT; and International Normalized Ratio/INR within 7 days of Day 1.
- d) Complete CBC and differential and peripheral blood lymphocyte subset and immunoglobulin levels (within 7 days of registration).
- e) Flow cytometry assessment for peripheral CLL cells and lymphocyte subpopulations (CD3, CD4, CD8, CD19,CD16/56 cells) within 7 days of Day 1.
- f) Within one month from registration. Bone marrow will be evaluated by flow cytometry for clonality and for IgVH mutation studies (unless known) ZAP-70 expression (unless known), cytogenetic and genomic abnormalities by FISH.
- g) Within one month
- h) CT scans of the chest , abdomen and pelvis within two months from Day 1.
- i) q) Optional correlative laboratory studies (blood samples) will be done before study entry, and after weeks 1, 2, 3, 4 (+/- 3 days).

Treatment Plan						If Patient Stays on Study past 12 Cycles		
Procedure	Day 7, 14, 21, 28 (+/-3 Days)	Cycle 2, 3, 4, 6, 9, 12 (+/-1 month)	Cycle 1,3,6,12 (+/- 1 month)	Cycles 1,6,12 (+/- 1 month)	Cycles 3,6, 12 (+/- 1 month)	Cycles 13-36 every 3 months (+/- 1 month)	Follow Up After Cycle 36 every 6 months (+/- 1 month)	Once every 12 cycles (+/- 1 month)
Clinical Visits at UT MD Anderson Cancer Center ⁱ	X	X				X	X	
Hematology and Serum Chemistry ^j	X ^k					X	X	X
PT, PTT, INR			X ^l					X
Beta-2-microglobulin, lymphocyte subset, immunoglobulin levels ^m					X			X
Bone Marrow Aspiration ⁿ					X			X
CT Scans ^o					X			X
Optional Quality of Life Questionnaire ^p			X					
Optional correlative laboratory studies (blood samples) ^q	X	X ^r						

